Device	
Description: Abbott's transcatheter, self-expanding AMPLATZER™ LAA Occluders are made of nitinol mesh and a polyester patch. The lobe has stabilizing wires placed within the left atrial appendage (LAA) and a disc (to cover the LAA orifice) connected to the lobe by a central waist. The AMPLATZER™ Cardiac Plug™ and the AMPLATZER™ Amulet™ LAA Occluders are currently available in the following sizes:
 
Sizes (lobe diameter):
 
 • 16, 18, 20, 22, 24, 26, 28 and 30 mm for the AMPLATZER™ Cardiac Plug™ • 16, 18, 20, 22, 25, 28, 31 and 34 for the AMPLATZER™ Amulet™ 
Future generation AMPLATZER™ LAA Occluders may be used in the study upon approval by Health Canada.
 
Delivery System: AMPLATZER TorqVue™ 45x45 (sheath sizes 9,10,12,13 and 14 Fr)

Indications for Use	Abbott's AMPLATZER™ LAA Occluders are intended to prevent thrombus embolization from the left atrial appendage (LAA) in patients who have non-valvular Atrial Fibrillation (AF). The device may be considered for use in patients who have a high risk of stroke and bleeding and are deemed by their physician to have an appropriate rationale to seek a non-pharmacologic alternative to long term anticoagulants.
Study Objective	To compile real world outcome data on the use of the AMPLATZER LAA Occluder in subjects with non-valvular atrial fibrillation.
Study Design	This is a non-randomized multicenter study on patients who have undergone a procedure to implant an AMPLATZER LAA Occluder or will undergo an implant of an AMPLATZER LAA Occluder.
Randomization	Non-randomized
Sample Size	This study, and other AMPLATZER LAA Occluder post approval studies collecting similar data, will contribute to the overall sample size of 1000 subjects for analysis of study endpoints. Up to 100 sites worldwide will participate in this study.
Primary Endpoints	
This study has three primary endpoints:
 
 • Efficacy Endpoint 1: The occurrence of the composite of stroke (including ischemic or hemorrhagic), systemic embolism, or cardiovascular or unexplained death at 24 months from the time of enrollment • Efficacy Endpoint 2: The occurrence of ischemic stroke or systemic embolism at 24 months from the time of enrollment • Safety Endpoint: The occurrence of one of the following events between the time of implant and within 7 days of the procedure or by hospital discharge, whichever is later: all-cause death, ischemic stroke, systemic embolism, or device or procedure-related events requiring open cardiac surgery or major endovascular repair
Secondary Endpoint	Comparison of the observed rate of ischemic stroke at 24months with the CHA ₂ DS ₂ -VASc predicted rate.
Descriptive Endpoints/Outcomes Measures	
The following endpoints will be summarized descriptively:
 
 • Oral anticoagulant use over time • Device closure at the 2 month visit

	
 • Procedural success • Technical success • Procedure duration • Device thrombosis • Transient ischemic attack • Death • Major bleeding
Enrollment Criteria	
Prospective Enrollments Patients in whom an AMPLATZER LAA Occluder device is intended to be implanted
 
Retrospective Enrollments Patients who underwent an AMPLATZER LAA Occluder implant attempt after the device was approved in the applicable geography

Clinical Follow-up Visits/Testing	
Subjects will be followed through 2 years post implant.
 
Required Testing for Prospective Enrollments
 
 • Baseline evaluation: Informed consent, history and physical, pregnancy testing for women of childbearing age, CHA2DS2-VASc score, HAS-BLED score, modified Rankin Scale, medication assessment • Procedure: Transesophageal echocardiogram (TOE), angiogram, adverse event assessment • Post procedure/Pre-Discharge: Transthoracic echocardiogram (TTE), medication assessment, adverse event assessment • 2M (+/- 45 days): TOE, medication assessment, adverse event assessment • 6M (+/- 4 weeks): Phone contact follow-up for medication assessment, adverse event assessment • 12M (+/- 6 weeks): Medication assessment, adverse event assessment • 2yrs (+/- 12 weeks): Medication assessment, adverse event assessment • Interim/unscheduled visits: per physician discretion 
Retrospectively enrolled subject data collection will include adverse events and standard of care (SOC) echo data previously collected by the site. Protocol required follow up visits will begin upon subject consent

Suspected Stroke / TIA Requirements	
 • Subjects suspected of a stroke should be seen by a stroke/TIA neurologist for evaluation and appropriate baseline neurological testing (i.e. magnetic resonance imaging (MRI), computed tomography (CT)) • Modified Rankin Scale • TOE or ICE should be conducted within 7 days of confirmation of stroke to verify the presence of device related thrombus

1.1 Study Contacts

Clinical Department, LAA Program
Abbott
Global Clinical Affairs
[name]
[name]
USA

████████████████████
████████████████████

2. Introduction

This document is a clinical investigational plan for St. Jude Medical's AMPLATZER™ Cardiac Plug™ and AMPLATZER™ Amulet™ Left Atrial Appendage (LAA) Occluders (these devices are referred to as "AMPLATZER LAA Occluder"). The study is a post-approval study to compile real world outcome data on the use of AMPLATZER LAA occluders in patients with non-valvular atrial fibrillation who are at increased risk for stroke and systemic embolism. This is a worldwide study intended to fulfill Health Canada's post-approval requirements for the device. Future generation AMPLATZER™ LAA Occluders may be used in the study upon approval by Health Canada. A patient who was either implanted or had an attempt to implant with an AMPLATZER LAA Occluder may be retrospectively enrolled in the study if the device was approved in the applicable geography at the time of the procedure.

3. Background and Justification

Atrial fibrillation (AF) is the most common sustained heart rhythm disorder¹. During AF there are multiple simultaneous waves of contractions, which spread in a chaotic manner through both atria. This arrhythmia results in rapid, uncoordinated contractions, which decrease the blood pumped through the atria. The loss of mechanical efficiency during AF leads to insufficient contractions in the left atrium (LA)². Stagnation of blood flow in the LA leads to hypercoagulability and thus increases the risk for thrombus formation in the LA or left atrial appendage (LAA). Approximately 90% of all the thrombi in subjects with non-valvular AF (NVAf) forming in the LA originate in the left atrial appendage³. The thrombus formation, in turn exposes the patient to thromboembolic events.

Echocardiographic risk factors for LAA thrombus formation include echocardiographic evidence of decreased LAA flow velocity and spontaneous echo contrast within the left atrium and left atrial appendage^{4,5}. The normal flow pattern of the LAA is the ejection of blood from the appendage following atrial contraction at a velocity greater than 40cm/s². Agmon et al. found that the relative risk reduction of ischemic stroke was 2.6 times greater in patients with LAA flow velocities <20cm/s² than those with higher LAA velocities⁶.

Non-valvular AF patients have been assessed to determine the risk of stroke based on the presence of independent risk factors. In a study by Gage et al. the CHADS₂ index was shown to be a tool to predict the risk of stroke in subjects with AF⁷. The CHADS₂ score assigns one point each for the presence of congestive heart failure, hypertension, age greater than 75 and diabetes mellitus and two points for history of stroke or transient ischemic attack (TIA). The study found that AF patients who were not treated with anti-thrombotic agents had an increased risk of stroke ranging from 1.9% to 18.2% as CHADS₂ scores increase from 0 to 6.

A study by Go et al. reviewed outcome data (11,526 patients) in a large primary care setting and confirmed that thromboembolic risk increases progressively with CHADS₂ score⁸. The study also noted that oral anticoagulation with warfarin reduces the risk of stroke in most patients with the exception of those at lowest risk (CHADS₂ score of zero) and highest risk (CHADS₂ >5) for stroke. The more recently developed CHA₂DS₂-VASc risk assessment scheme⁹, which identifies truly low risk subjects, assigns two points to age ≥75 years and previous stroke, TIA or thromboembolism and one point each to congestive heart failure or left ventricular dysfunction, hypertension, diabetes, vascular disease, age between 65-74 years and female sex. A recent validation¹⁰ of these risk schemes in more than 90,000 patients without oral anticoagulation (OAC) but on aspirin showed annual ischemic stroke rates ranging from 0.6% in CHA₂DS₂-VASc = 1 to 4.8% in CHA₂DS₂-VASc = 4, and more than 12% for CHA₂DS₂-VASc = 9.

In a meta-analysis conducted by Andersen et al., warfarin was found to be superior to aspirin and placebo in reducing the risk of systemic embolism in subjects with NVAf¹¹. Hart et al. reported that adjusted dose warfarin reduces stroke by 64% (6 trials) and antiplatelet agents reduce stroke risk by 22%¹². The study also reported that risk of intracranial hemorrhage was doubled with adjusted-dose warfarin compared with aspirin.

Recently, new drugs (known as novel oral anticoagulant, or NOAC) have been developed with less dietary and pharmacological interactions than warfarin and less stringent requirements for frequent INR monitoring. Major trials such as RE-LY and ROCKET AF demonstrated that dabigatran and rivaroxaban are non-inferior to warfarin in the prevention of stroke or systemic embolism^{13, 14}. The ARISTOTLE trial demonstrated Apixaban was superior to warfarin in preventing stroke or systemic embolism, caused less bleeding, and resulted in lower mortality in subjects with atrial fibrillation¹⁵. The ENGAGE AF-TIMI¹⁶ trial demonstrated both once daily dose regimens of Edoxaban were non-inferior to warfarin with respect to the preventions of stroke or systemic embolism and were associated with significantly lower rates of bleeding and death from cardiovascular causes¹⁷. A number of characteristics that increase a patient's risk for stroke also increase the patient's risk for bleeding; therefore an alternative to warfarin and NOAC drugs is needed.

Left atrial appendage occlusion (LAAO) is considered a viable alternative to oral anticoagulation (OAC) therapy for stroke prevention in patients with NVAf¹⁵⁻²⁵. Published evidence supporting LAAO is provided in large part by the major randomized controlled trials PROTECT AF and PREVAIL¹⁵⁻¹⁸. Five-year results of PROTECT AF showed superiority of the WATCHMAN™ device in mortality and stroke reduction compared to optimal medical treatment with warfarin¹⁸.

The AMPLATZER Cardiac Plug demonstrated favorable feasibility and safety in observational studies in Europe²⁶⁻²⁸. Additionally, Park et al. reported the results of an investigator-initiated retrospective study to report on the initial European experience in patients treated with the AMPLATZER Cardiac Plug device between December 2008 and November 2009. SJM's AMPLATZER Cardiac Plug Registry results were also presented at EURO PCR in 2012 and 2014²⁹⁻³⁰. In addition, results from a multicenter study involving 22 sites and 1047 consecutive patients undergoing implant of the AMPLATZER Cardiac Plug device showed a high procedural success rate and a favorable outcome for the prevention of AF related thromboembolism³¹.

In a comparative study between the AMPLATZER Cardiac Plug and the WATCHMAN devices (40 patients each), Chun et al.³² found the devices to perform similarly. The rate of successful implantation achieved with the ACP device was greater than with the WATCHMAN device (100% vs. 95%) although the difference was not statistically significant. TEE at follow-up revealed a significantly higher incidence of residual peri-device flow (jet > 5 mm) for the WATCHMAN device compared to the ACP device, although this was not associated with an increased incidence of thromboembolic events. This finding is consistent with other reports on the ACP device³³.

In conclusion, percutaneous LAAO devices have emerged as an alternate option for stroke reduction in non-valvular AF patients at high risk for stroke.

**See Appendix A for a listing of abbreviations used throughout this document*

4. Study Design

4.1 Purpose

The AMPLATZER LAA Occluders are transcatheter, self-expanding nitinol devices intended for use in preventing thrombus embolization from the LAA. The purpose of this study is to compile real world outcome data on the use of an AMPLATZER LAA Occluder in subjects with non-valvular atrial fibrillation (NVAf).

4.2 Study Design and Scope

The AMPLATZER LAA Occluder devices will be clinically evaluated through this post approval study. This is a multicenter, non-randomized observational post-approval study in subjects who meet one of the following criteria:

Prospective Enrollments

Patients in whom an AMPLATZER LAA Occluder device is intended to be implanted

Retrospective Enrollments

Patients who underwent an AMPLATZER LAA Occluder implant attempt after the device was approved in the applicable geography

4.2.1 Subject population

The subject population will include participants that are ≥ 18 years old and diagnosed with NVAf.

4.2.2 Number of study subjects

This study, and other AMPLATZER LAA Occluder post approval studies collecting similar data, will contribute to the overall sample size of 1000 subjects for analysis of study endpoints. Up to 100 sites worldwide, will participate in this study. [REDACTED]

4.2.3 Enrollment period and study duration

4.3 Endpoints

4.3.1 Primary endpoints

This study has three primary endpoints:

1. Efficacy Endpoint 1: The occurrence of the composite of stroke (including ischemic or hemorrhagic), systemic embolism and cardiovascular or unexplained death at 24 months
2. Efficacy Endpoint 2: The occurrence of ischemic stroke or systemic embolism at 24 months
3. Safety Endpoint: The occurrence of one of the following events between the time of implant and within 7 days of the procedure or by hospital discharge, whichever is later: all cause death, ischemic stroke, systemic embolism, or device or procedure-related events requiring open cardiac surgery or major endovascular repair*

* NOTE: Percutaneous catheter drainage of pericardial effusion, snaring of an embolized device, thrombin injection to treat femoral pseudoaneurysm and nonsurgical treatments of access site complications will not be included in the assessment of the third primary endpoint.

4.3.2 Secondary endpoint

The secondary endpoint is a comparison of the observed rate of ischemic stroke at 24 months with the CHA₂DS₂-VASc predicted rate.

4.3.3 Descriptive Endpoints/Outcomes Measures

The following endpoints will be summarized using descriptive statistics.

- Oral anticoagulant use over time
- Device closure
 - Defined as residual jet around the device ≤ 5 mm at the 2-month visit documented by transoesophageal echocardiogram (TOE)
- Procedure success
 - Procedural success-defined as implantation of the AMPLATZER LAA Occluder with no serious adverse events prior to hospital discharge
- Technical success
 - Technical success-defined as delivery and release of the AMPLATZER LAA Occluder.
- Procedure duration

- Device thrombosis
- Transient Ischemic Attack
- Death
- Major bleeding defined as Type 3 or greater based on the Bleeding Academic Research Consortium (BARC - **Appendix H: Major Bleed classification/definition**)

4.4 Enrollment Criteria

This study will enroll patients in whom an AMPLATZER LAA Occluder device is either intended to be implanted or underwent an implant attempt after the device was approved in the applicable geography

All patients who sign the informed consent will be assigned a study identification number and this will be recorded on a baseline electronic case report form (eCRF). The subject ID number will be unique to each individual and will allow the participant to be linked if necessary, to name, alternative identification or contact information. To ensure subject privacy and confidentiality of data, subject ID numbers will be used and maintained by study site personnel for the duration of the study.

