4.5 Informed Consent Process

The process for obtaining informed consent must comply with the ethical principles defined in the current version of the Declaration of Helsinki (**Appendix C**).

Prior to enrollment in the clinical study, all subjects will be consented, as required by applicable regulations and the site's Institutional Review Board (IRB) or ethics committee (EC). The consent form must be signed and dated by the subject and by the person obtaining the consent, where applicable.

The principal investigator (PI) or his/her authorized designee will conduct the informed consent process. This process will include a verbal discussion with the subject on all aspects of the clinical study that are relevant to the subject's decision to participate, and the subject should be allowed adequate time to review and ask questions.

Documentation that informed consent was obtained will be recorded on the eCRF and in the subject's medical record. The signature date on the consent form should be referenced. The original signed informed consent should be filed in the subject's study chart and a copy of the signed consent form given to the subject per IRB/EC requirements.

A template of the informed consent form is provided in **Appendix E: Sample Informed Consent**. Any changes to the informed consent must be approved by Abbott prior to ethics committee review and approval.

A subject cannot be consented for the study prior to IRB/EC approval of the informed consent form. The subject shall be provided the informed consent form that is written in a language understandable to the subject and has been approved by the site's IRB/EC.

The subject is enrolled in the study when consent has been obtained and vascular access initiated, (prospective), or when consent is obtained after a subject underwent a study device implant attempt that may have been successful or unsuccessful (retrospective). Failure to obtain informed consent from a subject must be reported to the Sponsor within 5 working days and to the reviewing center's IRB/EC according to the IRB/EC's reporting requirements.

5. Device

[figure not shown]
[figure not shown]

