5.2 Device Accountability

The AMPLATZER LAA Occluder devices are market released in the countries where this study will be conducted. Therefore, there are no tracking requirements for this study. Information regarding opened, introduced, and implanted devices will be recorded on the Procedure and Product Out of Service (where applicable) eCRFs.

6. Study Procedures

This study will be conducted in accordance with the clinical protocol and IFU. All persons participating in the conduct of the study will be qualified by education, training, or experience to perform study-related tasks.

The study will not commence at each selected site until Abbott receives written approval from the IRB/EC and relevant regulatory authorities, and all required documents have been collected from the participating sites.

Figure 3 below describes the study flowchart for subject screening, consent, enrollment and follow-up through the 2-year follow-up visit. **Table 2** outlines the testing and assessments required per study visit interval for subjects who are implanted with an AMPLATZER LAA Occluder.

Figure 3: Study flowchart for subject screening, consent, enrollment and follow-up

[figure not shown]
[figure not shown]
[figure not shown]

Table 2: Study visits and assessments (subjects who are implanted with an AMPLATZER LAA Occluder)

Follow up visit timing begins from the date of the procedure for both prospective and retrospective enrollments.

The electronic Case Report Forms (eCRFs) to be completed for enrolled subjects per the study visit intervals are:

- Baseline – Baseline, Enrollment, Modified Rankin Scale, Medication, and Echo
- Procedure – Procedure, Echo, Medication
- Discharge, 2M, 6M, 12M and 24M – Follow-up, Echo (as required), Medication
- Unscheduled visit - Follow-up, Medication, Echo (as required)

For retrospective enrollments, the applicable Baseline, echo, and adverse events CRFs should be retrospectively completed based on information from the subject's medical records. Retrospective data should include any adverse events from the date of implant or attempted implant. Protocol required follow up visits will begin after the subject's trial enrollment date.

Additional eCRFs, reports and assessment noted below should be completed upon occurrence, and/or as applicable:

- Withdrawal eCRF
- Adverse Event eCRF
- Protocol Deviation eCRF
- Death eCRF
- Stroke/TIA Assessment eCRF
- Echo eCRF

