6.1 Screening/Enrollment/Baseline

The following baseline and enrollment activities are performed as part of the screening process:

- Informed consent process
- History and physical
- Cardiovascular and medical exam
- Pregnancy testing for women of childbearing age
- TOE (optional if a TOE is performed on the day of procedure)
- Modified Rankin Scale
- Medication assessment
- CHA₂DS₂-VASc score:

Table 3: CHA₂DS₂-VASc score

CHA₂DS₂-VASc	Score
Congestive heart failure/LV dysfunction	1
Hypertension	1
Age > 75	2
Diabetes mellitus	1
Stroke/TIA/TE	2
Vascular disease [prior myocardial infarction, peripheral artery disease or aortic plaque]	1
Age 65-74	1
Sex category [i.e. female gender]	1

- HAS-BLED score:

Table 4: HAS-BLED score

HAS-BLED	Score
Hypertension history (uncontrolled, > 160 mmHg systolic)	1
Abnormal renal function/renal disease (dialysis transplant, creatinine > 2.6 mg/dL or > 200µmol/L)	1
Liver disease (cirrhosis, bilirubin > 2x normal AST/ALT/AP > 3x normal)	1
Stroke history	1
Bleeding, anemia, or predisposition to bleeding	1
Labile INR (Unstable/high INR's, or poor time (< 60% time in therapeutic range))	1
Elderly - Age ≥ 65 years	1
Drugs - Medication usage predisposing to bleeding (antiplatelet agents, NSAIDs)	1
Alcohol usage history (> 8 drinks/week)	1

The principal investigator or delegated study personnel is responsible for screening potential subjects to determine subject eligibility for the study. Enrollment information (date of consent, enrollment criteria, etc.) will be recorded in the subject's hospital records and on the Baseline eCRF. For prospective subjects, the Baseline eCRF should be submitted within one week of signing the informed consent form. Baseline eCRFs for retrospectively enrolled subjects will capture data before attempted implant, collected from their medical history.

For prospective subjects, if a subject does not meet criteria for AMPLATZER LAA Occluder implant, the subject cannot participate in the study. The Baseline eCRF (consented screen failure), as applicable, must be completed and the subject should be withdrawn. If the subject was enrolled (i.e. consented and vascular access initiated), but does not get a device implanted due to anatomy or other reason, the Baseline, Procedure, and Withdrawal eCRFs should be completed.

Serious adverse events will be reported from the time vascular access was initiated to the time the subject concludes the study. Adverse Event eCRFs should be completed, as applicable.

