14.1 Primary Endpoints

There are three primary endpoints, two effectiveness endpoints and one safety endpoint.

14.1.1 Primary Effectiveness Endpoint 1:

Primary effectiveness endpoint 1 is the occurrence of the composite of stroke (including ischemic or hemorrhagic), systemic embolism, or cardiovascular or unexplained death at 24 months.

Hypothesis:

Ho: $\lambda_1 \geq 9.6\%$

Ha: $\lambda_1 < 9.6\%$,
where λ_1 is the rate of primary composite endpoint 1 at 24 months.

Analysis Methods:

Kaplan-Meier analysis will be used to estimate the event rate of at 24 months (731 days post implant). The 97.5% upper confidence bound for the event rate must be less than 9.6% in order to declare success. [REDACTED]

Analysis Population:

Subjects in this study who receive an implant of the AMPLATZER LAA Occluder will be included in the analysis.

14.1.2 Primary Effectiveness Endpoint 2:

Primary effectiveness endpoint 2 is the occurrence of the composite of ischemic stroke or systemic embolism at 24 months.

Hypothesis:

Ho: $\lambda_2 \geq 6.6\%$

Ha: $\lambda_2 < 6.6\%$,

where λ_2 is the rate of primary composite endpoint 2 at 24 months.

Analysis Methods:

Kaplan-Meier analysis will be used to estimate the rate of event at 24 months (731 days post implant). The 97.5% upper confidence bound for the event rate must be less than 6.6% in order to declare success. [REDACTED]

Analysis Population:

Subjects in this study who receive an implant of the AMPLATZER LAA Occluder will be included in the analysis.

14.1.3 Primary Safety Endpoint:

The primary safety endpoint is the occurrence of one of the following events between the time of implant and within 7 days of the procedure or by hospital discharge, whichever is later: All-cause death, ischemic stroke, systemic embolism, or device or procedure related events requiring open cardiac surgery or major endovascular repair (percutaneous catheter drainage of pericardial effusion, snaring of an embolized device, thrombin injection to treat femoral pseudoaneurysm, and nonsurgical treatments of access site complication will not be included in the assessment of the third primary endpoint).

Hypothesis:

Ho: $P \geq 2.66\%$

Ha: $P < 2.66\%$,

where P is the proportion of subjects experiencing a primary safety event within 7 days of the procedure or by hospital discharge, whichever is later.

Analysis Methods:

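### Sites may enroll retrospective patients after the outcome is known, and the visible text has no consecutive-patient rule or log of attempts not enrolled, so the single-arm rates can be biased toward success

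*Protocol*

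**What the plan says.** Protocol 4.4 takes patients in whom the device is "either intended to be implanted or underwent an implant attempt after the device was approved in the applicable geography"; Section 4.2 and the synopsis give the same criterion. Section 4.5 places retrospective enrollment at the point "when consent is obtained after a subject underwent a study device implant attempt that may have been successful or unsuccessful (retrospective"). It gives no limit on the time since the attempt.

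Selection is left to the site in 6.1: "The principal investigator or delegated study personnel is responsible for screening potential subjects to determine subject eligibility for the study". The screen-failure form described there is for prospective patients who signed consent. It records nothing about a past attempt whose patient was never approached.

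Events before consent are collected. Section 6, after Table 2, says: "Retrospective data should include any adverse events from the date of implant or attempted implant". Section 6.4 repeats this for retrospective subjects and times their later visits from the implant date.

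Section 14.1 runs the effectiveness clock from implant: "Kaplan-Meier analysis will be used to estimate the event rate of at 24 months (731 days post implant"). Success for Effectiveness 1 is stated as "The 97.5% upper confidence bound for the event rate must be less than 9.6% in order to declare success", and for Effectiveness 2 as "The 97.5% upper confidence bound for the event rate must be less than 6.6% in order to declare success". The safety goal is 2.66%, tested with an exact binomial bound. SAP 2.3.1 takes all three goals from a US post-approval study of another manufacturer's device.

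Two places disagree with this picture. The synopsis starts the effectiveness clock at enrollment: "The occurrence of ischemic stroke or systemic embolism at 24 months from the time of enrollment". SAP 1.3 describes a prospective study of subjects who are still to be implanted and does not mention retrospective entry.

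**The concern.** When a site decides which past patients to approach, the chart already shows who has had a stroke, an embolism or a repair operation. On the Section 14 clock those events count if the patient is enrolled and vanish if the patient is not approached. The patients at issue are alive and able to consent. Loss of patients who died before consent is a separate route to bias.

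There is no control arm in which the same selection would occur, so any shortfall of events passes directly into the comparison with the goal. Event adjudication reaches enrolled subjects only, and SAP 2.8 imputes nothing. Protocol 14.4 says that no compromising factor is foreseeable, so the plan does not prepare the reader for this one. What is at stake is whether a rate below the goal reflects the device or the choice of patients.

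**Working it through.** **The plan's own figure.** The overall 1000 subjects (Protocol 4.2.2, shared with other post-approval studies) cannot be reproduced, because SAP 2.4 is redacted. It is used here only as the sample size.

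**Passing limits at n = 1000.** I sought the largest event count whose 97.5% upper bound lies below each goal, using the exact binomial bound:

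- Effectiveness 1 (9.6%): 77 events give 9.53% and 78 give 9.64%, so the limit is 77.
- Effectiveness 2 (6.6%): 50 events give 6.54% and 51 give 6.65%, so the limit is 50.
- Safety (2.66%): 16 events give 2.59% and 17 give 2.71%, so the limit is 16.

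A log-log Kaplan-Meier bound without censoring gives the same 77 and 50. A plain Wald bound would give 79 and 52.

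**No selection.** With the true rate at the goal, the chance of wrongly passing is P(X ≤ limit): 2.1%, 2.1% and 1.8%. All are within the intended 2.5%.

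**Selection model (all inputs are assumptions; the documents give none of them).**

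- p: true rate.
- f: retrospective share of the 1000.
- r: enrollment rate of patients with a known event relative to all others.
- q: share of events that are selectable, meaning known before consent.

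Effective ratio: r' = 1 − q(1 − r). Retrospective rate: p·r' / (p·r' + 1 − p). The pass probability comes from the sum of two binomials, 1000f subjects at that rate and 1000(1 − f) at p.

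**Effectiveness 2, p = 6.6%, r = 0.7, limit 50:**

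| q | r' | Retrospective rate | Wrongly pass, f = 50% | Wrongly pass, f = 100% |
|---|---|---|---|---|
| 25% | 0.925 | 0.06105/0.99505 = 6.14% | 4.0% | 7.3% |
| 50% | 0.85 | 0.0561/0.9901 = 5.67% | 7.4% | 20% |
| 100% | 0.70 | 0.0462/0.9802 = 4.71% | 20% | 70% |

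**Effectiveness 1, p = 9.6%, r = 0.7, limit 77.** The composite includes deaths, which this route does not select on. If half of the events are selectable non-fatal ones, r' = 0.85 and the retrospective rate is 0.0816/0.9856 = 8.28%. The chance of wrongly passing is 9.2% (f = 50%) or 28% (f = 100%).

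**Small values.** With f = 10%, r = 0.9 and every event known before consent, the chance is 2.5% for Effectiveness 2 and 2.6% for Effectiveness 1.

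**The case against.** The strongest objection is about size. Retrospective subjects continue protocol visits after consent, and an event after consent cannot influence who was approached. Treating every 24-month event as selectable gives only the extreme row of the table. This stands, and it is why the share before consent is shown as a range. The pooling of the 1000 with other studies also makes an all-retrospective sample an upper bound rather than an expected case.

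A second objection is that part of the text cannot be seen: Section 4.2.3, the end of 4.2.2, Figure 3, and SAP 2.1 and 2.9. A reader might infer that the plan has no implant-date range and no cap on the retrospective share. The documents do not support that, since either could sit there. What can be said is that 4.2, 4.4 and 4.5 are readable and contain no consecutive-patient rule and no log.

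Third, a reader might infer that no later analysis could repair the problem. That is too strong. Consent and procedure dates are recorded, so a prospective-only analysis, or delayed entry at consent with earlier events excluded, deals with selection on effectiveness events known at consent.

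Fourth, on the synopsis clock a stroke before consent would not be an endpoint event, and on the SAP's description there would be no retrospective subjects. These are contradictions to reconcile rather than defences. Section 14 and the retrospective data rules in Section 6 point the other way.

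**Conclusion.** The concern holds as a risk of bias toward success. The visible plan gives sites the opportunity to select on outcome, and the Section 14 clock makes that selection count. Whether it happens, and by how much, is unknown. A reader might infer that the observed rates will fall below the goals, but that needs a retrospective share, a selection ratio and a true rate that the documents do not give.

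Under the stated assumptions (1000 subjects, true rate at the goal, ratio 0.7), the false-pass chance for Effectiveness 2 rises from 2.1% to between 4.0% and 20% with half the subjects retrospective, and to between 7.3% and 70% with all of them. For Effectiveness 1 with half of the events selectable, it is 9.2% or 28%. With a 10% retrospective share and a ratio of 0.9 it stays at about 2.5%. The change is worth making because the opportunity is plain and the remedy is cheap.

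**What to change.** **Protocol 4.4.** Each site that enrolls retrospectively fixes its range of implant dates before screening and approaches every patient with an attempt in that range. It keeps a de-identified log of all attempts with the reason for non-enrollment (declined, unreachable, died, other) and, where the ethics committee permits, event status. Event status matters because reasons alone cannot show whether omission was related to outcome.

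**SAP.** Report the enrolled fraction by site next to the primary results. Add a sensitivity analysis of each effectiveness endpoint in prospective subjects only, or with delayed entry at consent, and of the safety endpoint in prospective subjects only.

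**Reconcile** the synopsis clock with the 731 days from implant in Section 14, and the prospective design in SAP 1.3 with the retrospective entry in the protocol. If a date range or cap already exists in text that is not public, refer to it in 4.4.

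**Cost.** A short log per site, a protocol paragraph and a little more analysis, with no extra patients or tests. The sensitivity analyses will have wider intervals, and some ethics committees may allow counts only.
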